For the subgroup analysis on the effect on LDL cholesterol, we based the sample size calculation on data for over 75 years old patients from the Cholesterol Treatment Trialists' Collaboration (67). Based on an assumed mean LDL cholesterol concentration of 3.2 mmol/L and a standard deviation of 0.8 mmol/L for the statin stop group, a between-group difference in LDL cholesterol of 0.3 mmol/L can be detected at 80% power with a two-sided alpha of 0.05. As previously described, in the case of continuous outcomes, a trial with ~100 participants per treatment arm is considered a large trial, where baseline variables can be expected to be evenly distributed between treatment arms (68).

For the subgroup of patients undergoing cardiac CT scans and measurement of biomarkers at baseline, we based the sample size calculation on a superiority design where we test whether the treatment effect differs by baseline CAC. Based on an assumed CAC distribution from data in the MESA cohort for asymptomatic men and women over 75 years (69), an assumed increased risk per 1-standard deviation change of baseline CAC score on a logarithmic scale (70), 7% of participants with a CAC score of 0 (71), primary outcome event rate at 36 months as in the STREAM trial, and assumption of no treatment effect, we determined that a fixed sample size of 500 participants provides 80% power (with one-sided alpha of 0.05) to detect an interaction term odds ratio as small as 1.9, corresponding to a traditional relative risk estimate of 1.37 at an assumed event prevalence of 43%, since ORs are overinflated when the outcome is common.(72) The power for analyses using biomarkers on a continuous scale will be similar as or even higher than for CAC score, e.g. for NT-proBNP the simulation showed 80% power to detect a relative risk of 1.3 at a fixed sample size of 500 participants.

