ITT and PP analyses will be performed. The ITT analysis set consists of all randomized patients in the allocated group regardless of any protocol violations. For the PP analysis set, we will first carefully define criteria for protocol adherence and post-randomization factors that might cause confounding/selection bias before trial start to allow for appropriate data collection.(79) For this, we will consider pre- and post-randomization factors that are predictive of adherence, amount of statin intake that constitutes adherence to each arm, cross-overs, other CV active medication, and intercurrent events. PP analyses will be done using g-Methods adapted to estimate Restricted Mean Event-free Time (80).

A separate statistical analysis plan will be developed for the analysis of CAC scores and baseline blood biomarkers in the subsample of subjects undergoing these procedures. The primary analysis will be an ITT analysis using Cox proportional hazards regression modelling to assess the effect modification of continuous CAC score on a linear scale on the relationship between treatment and the primary outcome, taking event time into account. Further analyses will test non-linear relationships and/or include biomarkers instead of CAC score.

Any deviation from the original statistical analysis plan will be described and justified in the final trial report. Full details to the statistical analysis will be described in a statistical analysis plan.

[figure not shown]

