CAC score is recommended in some but not all practice guidelines for the CV risk assessment and reclassification in selected low- intermediate risk asymptomatic individuals.(33, 84) The predictive value of CAC scores is currently unknown in multimorbid older adults; even if shown to be predictive, there is currently no evidence from RCTs that an intervention (e.g. statin treatment) lowers CAC-related increased risk. The CAC score is a study specific measurement performed outside of a clinical indication; and deferred CAC score reporting to participants and physicians is favored for the following reasons: 1) There is clear equipoise surrounding the management of ASCVD risk in adults >70 years of age without clinically evident ASCVD; 2) There is uncertainty about the interpretation of risk as a function of CAC scores above age 70, including uncertain value of conventional score categories (i.e. CAC >100 as a marker of high risk, in a population where the 75th percentile is expected to be 400-1200) (85) and uncertain value of the traditional Agatston score (CAC density increases with age and results in higher CAC scores, yet increased CAC density is known to be a marker of stable, lower risk plaque (86)); 3) There is currently no compelling evidence to support the use of statins based on CAC scores to improve outcomes including death, cognition, and disability – the most important outcomes to multimorbid adults age >70; and 4) Reporting CAC scores during the study intervention period could influence participant behavior and might drive downstream testing (i.e. stress tests and cardiac catheterizations) that could lead to harm in patients without symptoms of cardiovascular disease.(87) Thus, CAC score reporting during the intervention phase of STREAM may influence the pharmacologic treatment (including statin therapy or intensity) and result in imbalanced cardiovascular testing, which would compromise the information obtained from the main trial.

The CAC CT scan area also comprises non-cardiac body parts, and incidental findings may be noted on these scans. A retrospective analysis of 966 patients that underwent cardiac CT scans found non-cardiac incidental findings in 41.5% of patients, with 12 (1.2%) patients with clinically significant findings (e.g., suspect pulmonary nodule, pulmonary infiltrates, thrombus) and 68

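### The CAC sub-study is powered on a logarithmic CAC scale, but its primary effect-modification analysis is specified on a linear scale, where power would be materially below the stated 80%

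*Protocol*

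**What the plan says.** Section 5.1 of the protocol sizes the CAC sub-study on "an assumed increased risk per 1-standard deviation change of baseline CAC score on a logarithmic scale", together with "7% of participants with a CAC score of 0", the 36-month event rate of the main trial and an "assumption of no treatment effect". From these it concludes that "a fixed sample size of 500 participants provides 80% power (with one-sided alpha of 0.05") is enough "to detect an interaction term odds ratio as small as 1.9". It then expresses the same effect on the risk-ratio scale, as "corresponding to a traditional relative risk estimate of 1.37 at an assumed event prevalence of 43" per cent. It does not give the size of the assumed CAC risk gradient, the median or spread of CAC, or the unit to which the interaction odds ratio refers.

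Section 5.3 announces a separate analysis plan for this sub-study but already fixes the primary model: an intention-to-treat Cox regression of the "effect modification of continuous CAC score on a linear scale on the relationship between treatment and the primary outcome". Non-linear relationships are left to further analyses. No log transformation is mentioned for the analysis.

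The only other distributional figure is in section 7.2, where conventional CAC cut-offs are doubted "in a population where the 75th percentile is expected to be 400-1200".

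**The concern.** The two sections name different scales for the same variable. The difference matters because CAC is far from symmetric: some participants score zero and a quarter are expected to exceed a value between 400 and 1200. On the raw scale most participants lie close together and the long upper tail supplies much of the information on the slope. If risk rises with log CAC, as section 5.1 assumes, a raw-scale interaction term fits that relationship poorly and the 80% no longer describes the test to be run.

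Section 3.1 makes this interaction the primary aim of the sub-sample: does risk after stopping the statin differ with the burden of subclinical atherosclerosis? An underpowered test could be taken as support for stopping regardless of CAC. The later non-linear analyses do not repair a primary test on an unsuitable scale, and choosing the scale after seeing the data would be post hoc.

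**Working it through.** **Inputs from the protocol.** N = 500, 1:1 allocation, one-sided alpha 0.05, interaction odds ratio (OR) 1.9, 43% events at 36 months, 7% zeros, 75th percentile of CAC 400–1200, control-group event probabilities 22%, 34% and 43% at 12, 24 and 36 months.

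**Step 1: the stated relative risk.** RR = OR / (1 − p + p × OR) = 1.9 / (0.57 + 0.43 × 1.9) = 1.9 / 1.387 = 1.370. This matches the stated 1.37.

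**Step 2: the stated 80%.** For a standardised covariate with no prognostic effect, the logistic interaction has SE = √(4 / (N p (1 − p))) = √(4 / (500 × 0.43 × 0.57)) = 0.181. Power for OR 1.9 is Φ(0.642 / 0.181 − 1.645), about 97%, and 80% would already be reached at OR 1.57. So the stated inputs alone do not fix the 80%. Adding an assumed prognostic OR of 1.8–2.0 per SD of log CAC brings simulated log-scale power at OR 1.9 to 77–89%. The 80% is therefore plausible on the log scale, given a prognostic effect that the protocol assumes but does not quantify.

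**Step 3: an approximation by hand.** Take a test with exactly 80% power on the log scale. Its expected z-value is 1.645 + 0.842 = 2.486. If the truth is linear in log(CAC+1) and raw CAC is fitted instead, the expected z shrinks roughly by the correlation r between raw and log CAC. The correlations below come from assumed log-normal scores with median 200 and 7% zeros; the resulting 75th percentiles (about 500 and 685) lie inside the protocol's 400–1200.

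| Assumed CAC tail | r | r × 2.486 − 1.645 | Power |
|---|---|---|---|
| log-SD 1.5, capped at 5000 | 0.64 | −0.05 | 48% |
| log-SD 1.5, uncapped | 0.52 | −0.35 | 36% |
| log-SD 2.0, uncapped | 0.43 | −0.58 | 28% |

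This ignores the prognostic effect, so simulation is needed for the rest.

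**Step 4: simulations.** The truth is linear in log CAC, and each data set is analysed once with log CAC and once with raw CAC. The Cox runs use a Weibull baseline through 22% and 43% at 12 and 36 months (shape 0.743; it returns 34.0% at 24 months, as stated). Not in the protocol and therefore assumed: median CAC 100–400, log-SD 1.2–2.5, scores capped at 5000–6000 or uncapped, and a prognostic effect of 1.0–2.0 per SD. With 600–800 runs per setting, as in the main Cox runs, Monte Carlo error is up to about 2 percentage points.

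| Setting | Log CAC | Raw CAC |
|---|---|---|
| Cox, interaction set for about 80%, prognostic CAC | 75–84% | 43–60% |
| Cox, same, no prognostic effect | 75–84% | 29–54% |
| Logistic, interaction set for about 80%, prognostic CAC | 75–84% | 58–63% |
| Logistic, same, no prognostic effect | 75–84% | 40–54% |
| Logistic, OR 1.9, prognostic OR 1.8–2.0 | 77–89% | 63–75% |
| Cox, interaction HR 1.42, uncapped | 67–81% | 27–44% |
| Cox, interaction HR 1.42, capped at 5000 | 67–81% | 45–56% |

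The last two rows share one log-scale range. The interaction hazard ratio (HR) of 1.42 is an assumption, not a protocol figure.

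**Step 5: false positives.** With prognostic log CAC and no interaction, the uncapped raw-scale Cox test rejected 12–14% of the time at a prognostic HR of 1.3 and 21–27% at 1.6. The logistic version gave 13–16%. The log-scale Cox test stayed at 4–7%. Capping scores at 5000 brought the raw-scale Cox rate back to about 5–8%. Part of the raw-scale power seen with uncapped scores is therefore misspecification rather than detection.

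**The case against.** The strongest reply is that a linear scale need not mean untransformed CAC. The next sentence of section 5.3 contrasts it with non-linear relationships, so the authors may have meant a continuous linear term first and curves later; a linear term in log CAC would fit that reading. This cannot be excluded. But the phrase as written describes the scale of the score, and an analyst following it would fit raw CAC. If log CAC was meant, the text still needs correcting.

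Second, section 5.1 attaches the logarithm to the assumed CAC risk gradient and does not give the unit of the interaction odds ratio. That the interaction was powered per SD of log CAC is an inference, though the natural one.

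Third, a separate analysis plan is announced. That would answer an omission. Here the protocol itself names a scale that differs from its planning scale.

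Two stronger readings are tempting. A reader might infer that power is halved. Around 40% or less does appear, chiefly with uncapped heavy tails or no prognostic effect, but the protocol gives neither the tail nor the size of the gradient, and other settings lose much less. A reader might also infer that a false finding of no effect modification becomes the likelier outcome. That needs power below 50%, whereas at the protocol's own OR of 1.9 with a strong prognostic effect raw-scale power is 63–75%. Neither follows from the document.

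**Conclusion.** The inconsistency stands: the power calculation uses a logarithmic CAC scale and the primary analysis names a linear one. If risk and its modification follow log CAC and raw scores are analysed, power falls materially below 80%: to about 30–60% in most assumed settings and up to about 75% in some. Where CAC is prognostic and its upper tail is heavy and uncapped, the type I error can also rise to about 12–27%. These ranges rest on assumed CAC distributions, prognostic effects and interaction units, so no single figure should be quoted as the protocol's true power. Severity and confidence are moderate. The point concerns the sub-study's primary aim and leaves the main non-inferiority comparison, safety monitoring and data collection untouched.

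**What to change.** In section 5.3 and in the separate CAC analysis plan, before the sub-study data are analysed, define the primary interaction as treatment by standardised log-transformed CAC with a prespecified offset for zero scores, for example log(CAC+1). This matches section 5.1. Keep raw-scale and spline forms as sensitivity analyses. In section 5.1, state the unit of the interaction odds ratio, the assumed prognostic effect and the assumed CAC distribution, so that the 80% can be reproduced. If raw CAC is really intended as primary, recompute and restate the power on that scale.

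The cost is a short wording change and no additional data. The downsides are small: the interaction is read per SD of log CAC rather than per Agatston unit, and the choice of offset has to be justified.

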5.4 Statistical methods for additional analyses

We perform subgroup analyses according to statin intensity and time on statin before baseline, sex, age, and degree of frailty, accompanied by appropriate tests for interaction. All subgroup analyses will be described in the statistical analysis plan.

5.5 Safety Interim Analysis

Formal interim analyses are performed to assess intervention safety (discontinuing statins). The main safety concern is increased risk of CV events in the experimental arm, therefore, the primary endpoint is monitored. We will take an event driven approach by conducting an analysis after a certain amount of events (in both arms combined) have accumulated and monitoring the proportion of events in the experimental arm. A one-sided boundary, calculated based on exact binomial tests with a pre-defined alpha that optimizes the stopping probability under different conditions, is used for decision-making. If there is evidence that the proportion of events in the experimental arm is higher than 50%, i.e. the boundary is crossed, the DSMB will be informed and an ad hoc meeting of the DSMB will be called to discuss possible termination of the trial for safety reasons. As there are concerns about those under 75, interim analyses will be performed separately for the two age groups, with lower boundaries used for younger group (making it more likely to stop the trial in this arm). Interim analyses will be performed after every 50th event in the older group and after the 50th event in the younger group (with only one look).

The following figure gives a fictional example for a trial with ca 700 events and interim analyses at each 100th event (indicated by the black lines). As the red line remains beneath the black lines, the trial could continue. This approach does not increase the type 1 error rate. The frequency of safety interim analyses and other details will be included in the statistical analysis plan.

5.6 Data and Safety Monitoring Board (DSMB) and Trial Steering Committee (TSC)

Safety is descriptively monitored throughout the trial by an independent DSMB. The DSMB members are unblinded and independent of the study team. Roles and responsibilities of the DSMB are described in a DSMB charter. Each DSMB member evaluates interim safety results. Based on these results, the DSMB recommends continuing, amending, or terminating the trial. The DSMB will meet after 600 and 1,200 participants have been recruited and ad hoc, when indicated as described in chapter 5.5.

The TSC consists of the sponsor-investigator and some experts in the fields of clinical trial management, statistics, geriatrics, statin intake, endocrinology, cardiology, and patient involvement. In addition, the principal investigators of the main participating trial sites are members of a General Assembly. The TSC will decide on the implementation of the recommendations of the DSMB following a DSMB review of the trial. The final decision to amend or terminate the trial lies with the TCS.

5.7 Handling of missing data and drop-outs

Depending on the extent of cross-overs and intercurrent events at the end of the trial, further analyses will model them, taking into account possible post-randomization confounding by using causal inference methods (81).

Very little missing data for either primary or secondary outcomes or important baseline covariates are anticipated. Generally, missing data on secondary outcomes will be handled with multiple imputation.

6 REGULATORY ASPECTS AND SAFETY

6.1 Local regulations / Declaration of Helsinki

This study is conducted in compliance with the protocol, the current version of the Declaration of Helsinki, ICH-GCP guidelines, the Swiss Human Research Act (HRA) as well as other locally relevant legal and regulatory requirements.

6.2 (Serious) Adverse Events and notification of safety and protective measures

An Adverse Event (AE) is any untoward medical occurrence in a patient or a clinical investigation subject which does not necessarily have a causal relationship with the trial procedure. An AE can therefore be any unfavourable or unintended finding, symptom, or disease temporally associated with a trial procedure, whether or not related to it.

A Serious Adverse Event (SAE) is any untoward medical occurrence that

- Results in death or is life-threatening,
- Requires in-patient hospitalisation or prolongation of existing hospitalisation,
- Results in persistent or significant disability or incapacity, or
- Causes a congenital anomaly or birth defect.

In this study, the follow-up assessment is carried out centrally by the team of the sponsor-investigator, without involvement of the local study sites. For this reason, the SAE assessment is only made by the sponsor-investigator (or delegate), also for patients who were included at a local site. The sponsor-investigator (or delegate) makes a causality assessment of the event to the trial intervention, (see table below). Any event assessed as possibly, probably, or definitely related is classified as related to the trial intervention.

Relationship	Description
Definitely	The adverse event is clearly related to the trial intervention. Clear-cut temporal association and no other possible cause.
Probably	The adverse event is likely related to the trial intervention. Clear-cut temporal association; a potential alternative aetiology is not apparent.
Possibly	The adverse event may be related to the trial intervention. Less clear temporal association; other aetiologies also possible.
Unlikely	The adverse event is doubtfully related to the trial intervention. Temporal association between the AE and the trial intervention and the nature of the event is such that the trial intervention is not likely to have had any reasonable association with the observed illness/event (cause and effect relationship improbable but not impossible).
Not related	The adverse event is clearly not related to the trial intervention. The AE is completely independent of trial treatment and/or evidence exists that the event is definitely related to another aetiology.

The sponsor-investigator (or delegate) makes an intensity assessment of the event. The intensity assessment is performed in accordance with “Common Terminology Criteria for Adverse Events (CTCAE), Version 5.0” terminology, using a grading scale from 1 to 5.

Reporting of SAEs (see ClinO, Art. 63)

If it cannot be excluded that the SAE is attributable to the intervention under investigation, the SAE is documented in a standardized manner and reported immediately (within a maximum of 24 hours) by the study team member who performs the follow-up assessment to the sponsor-investigator (or delegate). The period for documenting and reporting SAEs in this study is the study intervention period.

The sponsor-investigator (or delegate) reports these SAEs to the EC via BASEC within 15 days. If the SAE occurs at one of the study sites, the coordinating Investigator reports the events to the EC concerned, within 15 days.

Follow up of (Serious) Adverse Events

Reported ongoing SAEs are followed-up until resolution or stabilisation, even if the subject has already completed the study.

Notification of safety and protective measures (see ClinO, Art. 62, b)

If immediate safety and protective measures must be taken during the conduct of the study, the sponsor-investigator (or delegate) notifies the EC of these measures, and of the circumstances necessitating them, within 7 days.

6.3 (Periodic) safety reporting

An annual safety report (ASR) over all study sites is submitted once a year to the local EC by the sponsor-investigator (or delegate) (ClinO, Art. 62, d). The sponsor-investigator (or delegate) distributes the ASR to all local principal investigators.

6.4 Radiation

The CAC scan is a native CT scan only performed over the region of the heart, and the typical average radiation dose of a CAC scan is very low at 0.5-1.0 mSv (82), posing minimal risk for the subjects. For comparison, the worldwide average annual effective radiation dose from natural sources is about 3.1 mSv per person.(83) Total radiation dose for two CAC scans over the entire study duration will be max. 1.0 to 2.0 mSV.

If the permitted dose guidance value is exceeded at any time, the investigator notifies the Ethics Committee via BASEC within 7 working days of it becoming known.

6.5 Pregnancy

Not applicable.

6.6 Amendments

Substantial changes to the study setup and study organization, the protocol, and relevant study documents are submitted to the EC for approval before implementation. Under emergency circumstances, deviations from the protocol to protect the rights, safety, and well-being of human subjects may proceed without prior approval of the EC. Such deviations will be documented and reported to the EC as soon as possible.

A list of all non-substantial amendments will be submitted once a year to the competent EC together with the ASR.

6.7 (Premature) termination of study

The TSC may terminate the study prematurely according to the following circumstances:

- Ethical concerns,
- Insufficient participant recruitment,
- When the safety of the participants is doubtful or at risk (e.g. when the benefit-risk assessment is no longer positive), or
- Early evidence of harm of the experimental intervention based on safety interim analyses and respective recommendations by the DSMB.

Upon regular study termination, the EC is notified via BASEC within 90 days (ClinO, Art. 62, c).

Upon premature study termination or study interruption, the EC is notified via BASEC within 15 days (ClinO, Art. 62, c).

See chapter 8.4 for a detailed description of retention and archiving of study data and biological material.

